### 16. Corneal epithelium-specific antibody tests

Corneal epithelium-specific antibody tests were conducted using a partially modified method of a previous report. Cultured iCEPS in a 96-well plate were fixed with methanol ( $-30^{\circ}$ C) overnight or longer after removing the culture supernatants. They were subsequently washed three times with TBS, and permeabilised and blocked with TBS containing 1% BSA and 0·3% Triton X-100 for 1 h at room temperature. Serum samples collected preoperative and after surgery ( $\times$ 500) or commercially available (control,  $\times$ 500), Keratin-14 (positive control, 1 µg/mL, rabbit IgG, BioLegend), and isotype control rabbit IgG (negative control for Keratin-14, 1 µg/mL, Bio-Techne, Minneapolis, MN, USA) were used as primary antibodies. Additionally, iCEPS without primary antibodies (negative control for serum samples) was included. The iCEPS cells were incubated with or without primary antibodies at 4°C overnight, washed three times with 0·05% Tween in TBS for 10 min for serum samples and negative control for serum samples,

and stained with secondary antibodies for 1 h at RT (1–30°C). Alexa Fluor 488 anti-human IgG (20  $\mu$ g/mL, Thermo Fisher Scientific) was used as the secondary antibody in samples with serum as the primary antibody and in negative control samples without primary antibody. Alexa Fluor 488 anti-rabbit IgG (20  $\mu$ g/mL, Thermo Fisher Scientific) was used as the secondary antibody in samples with anti-Keratin-14 antibody as the primary antibody and in samples with rabbit IgG isotype control. Cell nuclei were counterstained with Hoechst 33342 (Merck Millipore, Burlington, MA, USA). Mean fluorescence intensity was measured using a high-content imaging system (Operetta, PerkinElmer, Waltham, MA, USA). A well containing only TBS without iCEPS was used as a blank control (Table S30).

### 17. Mixed lymphocyte reaction (MLR)

Blood samples were collected from the recipients to perform the MLR assay. Subsequently, peripheral blood mononuclear cells (PBMCs) were isolated from transplanted recipients as responder effector cells and co-cultured with single iCEPS cells as target cells for 7 days. As a positive control for allogeneic immune rejection, transformed B cells were prepared from HLA-mismatched healthy adult donors after obtaining informed consent. He culture medium and detailed methods were previously reported. Before the assay, B cells and single iCEPS cells were incubated for 45 min at 37°C with 50 μg/mL mitomycin C to inactivate their cell proliferative activity. The supernatants were harvested after 7 days and assessed for IFN-γ secretion using Quantikine Human IFN-γ ELISA Kit (R&D Systems, Minneapolis, MN, USA). Peripheral blood mononuclear cells and PBMCs co-cultured with single iCEPS cells or transformed B cells were harvested for flow cytometric analysis.

The harvested PBMCs In MLR were incubated with APC anti-CD4 antibody (Miltenyi Biotec, Bergisch Gladbach, Germany, catalog no. 130-091-232 or 130-113-250), APC anti-CD8a antibody (Thermo Fisher Scientific, catalog no. 17-0088-42), APC anti-CD11b antibody (Miltenyi Biotec, catalog no. 130-091-241 or 130-113-231), and FITC anti-CD56 antibody (BioLegend, catalog no. 304604) for 1 h at RT (1–30°C). Intracellular staining with PE anti-human Ki-67 antibody (BioLegend, catalog no. 350504) was performed using fixation and permeabilisation solutions (BD Cytofix/Cytoperm kit, BD Biosciences). All samples were analysed using a FACSVerse flow cytometer (BD Biosciences). Data were analysed using FlowJo software (BD Biosciences) (TableS31).

### 18. Statistical tests

Statistical tests were performed to compare preoperative and postoperative LSCD stage, corrected distance visual acuity (CDVA; decimal visual acuity) and corneal opacification at each visit of four patients using the Friedman test and a repeated measures ANOVA. The contrast setting was a comparison of eight preoperative and eight postoperative time points (2, 4, 8, 16, 24, 32, 40 and 52 weeks after transplantation) for repeated measures ANOVA, and the Bonferroni method was used for multiple comparisons. The F values with (1, 3) degrees of freedom and unadjusted P values of the test results are shown in tables S32-S34. The time points at which statistically significant differences were found are indicated by \*.

The Friedman non-parametric test demonstrated that there were significant differences in the LSCD stage, CDVA and corneal opacification values throughout the follow-up period (p-values of 0.001, 0.03 and 0.01, respectively). Despite the difficulty in demonstrating a normal distribution due to the limited number of cases in this study (n = 4), we performed a repeated measures ANOVA on the assumption that these outcomes follow a normal distribution, particularly visual acuity, which typically follows a normal distribution. To ensure that the pairwise comparisons in the post hoc analysis were conducted with the Bonferroni correction, we applied one of the strictest correction methods. Tables S32-34 in the supplementary appendix show the ANOVA data, which are consistent with those obtained by the aforementioned Friedman test.

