#### 13.2.4 Secondary endpoints (efficacy)

A time course of severity will be shown in a table and line graph for the following items defined in "9.2 Secondary Endpoints": 1) LSCD stage, 2) severity of corneal epithelial defect, 3) subjective symptoms, 6) degree of corneal opacification, 7) degree of corneal neovascularization, and 8) degree of symblepharon. For "4) Corrected distance visual acuity," measured values and the magnitude of change from baseline over time will be shown in a table and line graph. For "5) QOL," the 12-item subscale scores on the NEI VFQ-25 will be calculated, and the overall score will be calculated from 10 subscales excluding "general health" and "driving." In addition, summary statistics for overall score at baseline and at Week 52 after iCEPS transplantation or the discontinuation date will be calculated and evaluated. Baseline is defined as the day of transplantation (before transplantation).

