# 13.3 Significance Level To Be Used

No estimations or tests that would require setting of confidence coefficients or significance levels will be used in this research. Instead, descriptive methods will be used in analysis.

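### The Friedman p values do not show a preoperative-to-postoperative change, its direction or its persistence, and they do not corroborate the ANOVA contrasts against baseline

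*Combined protocol and SAP*

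**What the plan says.** Supplementary Methods 18 gives the purpose as a before-and-after comparison: "Statistical tests were performed to compare preoperative and postoperative LSCD stage, corrected distance visual acuity", together with corneal opacification, by the Friedman test and a repeated measures ANOVA. The follow-up consists of "eight postoperative time points (2, 4, 8, 16, 24, 32, 40 and 52 weeks after transplantation"), and the section acknowledges "the limited number of cases in this study (n = 4"). For the Friedman test it states: "The Friedman non-parametric test demonstrated that there were significant differences in the LSCD stage, CDVA and corneal opacification values throughout the follow-up period". The results for the three outcomes, taken in that order, are printed as "p-values of 0.001, 0.03 and 0.01, respectively". The section gives no test statistic, degrees of freedom, tie handling or rank-based follow-up comparison with baseline.

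The same section reports ANOVA contrasts of the preoperative value with each postoperative visit, as F on (1, 3) degrees of freedom with unadjusted P values. It closes by saying that these agree with the Friedman result.

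The protocol planned something else. Section 13.3: "No estimations or tests that would require setting of confidence coefficients or significance levels will be used in this research". Section 13.2.4 plans a time course in tables and line graphs for LSCD stage and opacification. For corrected distance visual acuity, "measured values and the magnitude of change from baseline over time will be shown in a table and line graph".

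**The concern.** The question is whether eyes were better after surgery than before. The Friedman null hypothesis is that the values at all visits are exchangeable within a patient. It can be rejected by a difference between any visits, in either direction, including a postoperative fluctuation that has gone by Week 52. A reader who sees p = 0.03 for visual acuity in a section introduced as a preoperative-versus-postoperative comparison may well take it as evidence that vision improved and stayed improved.

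The second problem is the role given to the test. The section concedes that normality is hard to show with four patients, then presents the ANOVA as agreeing with the non-parametric result. That makes the Friedman test the distribution-free backing for the baseline contrasts. A test of another hypothesis cannot do that work.

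**Working it through.** **Inputs.** n = 4 patients (Supplementary Methods 18). k = 9 time points: one preoperative value plus the eight visits listed there. The text speaks of eight preoperative points; I read this as one baseline compared eight times, which is an assumption. Reference distribution: chi-square on k − 1 = 8 degrees of freedom, 5% critical value 15.51. No significance level is stated for these tests, so 0.05 is also assumed.

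**The reported figures.** The Friedman p values cannot be reproduced, because the per-patient tables are not in the text reviewed. With 8 degrees of freedom, p = 0.001, 0.03 and 0.01 correspond to Q of about 26.1, 17.0 and 20.1.

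**Step 1: what Q responds to.** With r_ij the rank of visit j in patient i and R_j the rank sum, the tie-corrected statistic is

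Q = (k − 1) × Σ_j [R_j − n(k + 1)/2]² / Σ_ij [r_ij − (k + 1)/2]².

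Here (k + 1)/2 = 5. If all four patients show the same pattern, then R_j = 4r_j. The numerator sum is 16 × Σ(r_j − 5)², the denominator is 4 × Σ(r_j − 5)², and Q = 8 × 4 = 32 whatever the pattern. Three cases on a grade where higher is worse:

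| Pattern in all four patients | Ranks | Σ(r − 5)² | Q | p |
|---|---|---|---|---|
| Better at all eight visits | 9; 4.5 eight times | 16 + 8 × 0.25 = 18 | 8 × 288/72 = 32 | 0.0001 |
| Better at Weeks 2 and 4 only | 6 seven times; 1.5 twice | 7 + 2 × 12.25 = 31.5 | 8 × 504/126 = 32 | 0.0001 |
| Worse at Weeks 2 and 4 only | 4 seven times; 8.5 twice | 7 + 2 × 12.25 = 31.5 | 8 × 504/126 = 32 | 0.0001 |

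This needs no assumption about noise.

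**Step 2: with noise.** I simulated 40,000 trials per scenario with independent normal values, SD being the within-patient visit SD. With no preoperative-to-Week-52 difference and a shift at Weeks 2 and 4 only, the test rejects in 16%, 68% and 97% of trials for shifts of 1, 2 and 3 SD. A paired t test of preoperative against Week 52 stays at 5%. The shift sizes are illustrative, not estimates from this trial.

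**Step 3: the baseline contrasts.** One contrast table can be read: the last before the Supplementary References, without its heading. Recomputing P from F(1, 3) and multiplying by 8:

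| F | P | Bonferroni, 8 comparisons |
|---|---|---|
| 27.99 (three visits) | 0.013 | 0.105 |
| 17.64 | 0.025 | 0.197 |
| 16.36 (three visits) | 0.027 | 0.218 |
| 15.21 | 0.030 | 0.239 |

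The printed values of 0.01 to 0.03 are reproduced. An adjusted P below 0.05 would need F above about 47.5.

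**Step 4: the exact floor.** A two-sided sign-flip test of preoperative against any single visit has 2⁴ = 16 sign patterns, so its smallest p is 2/16 = 0.125. The smaller Friedman p values are therefore not a stronger version of that comparison.

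**The case against.** The strongest reply is that the Friedman test stands beside directed contrasts against baseline, a common pairing of an overall test with specific comparisons. The section claims only significant differences, not improvement. The readable contrast table also does not look like a transient effect. If its columns follow visit order, the Week 52 contrast is F = 17.64 with unadjusted P of 0.02, and the repeated F values suggest grades that stayed the same over several visits. For stable tied grades, a lasting change is a perfectly good reason for the Friedman test to reject.

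Much of that stands. A reader might infer from this point that the improvement was temporary. The documents do not support that: the readable table leans the other way, and the other two contrast tables are not available to check. But persistence would then be shown by the patients' values, not by the Friedman p value, which would be the same in either case. Nor do the readable contrasts rescue the inference, since none stays below 0.05 after the correction that the section itself invokes.

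A second tempting reading is that the Friedman test often misses a true lasting change. Without ties, a perfect step in all four patients contributes only 12/(4 × 9 × 10) × (16² + 8 × 2²) = 9.6 to Q, below 15.51, and simulated power levels off near 41%. That holds only for untied or noisy values. With stable tied grades, as LSCD stage and opacification may be, power is 100%. All three tests rejected, so lost power did no harm here.

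Finally, the conflict with section 13.3 concerns any testing at all and says nothing against the Friedman test in particular. It matters here because the p values are not labelled post hoc.

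**Conclusion.** The point holds as a limit on interpretation. The p values 0.001, 0.03 and 0.01 support the statement that values differed between at least two visits, and no more. They do not establish a preoperative-to-postoperative change, its direction or its presence at Week 52. They also do not corroborate the ANOVA contrasts.

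The result in Step 1 is exact given n = 4, k = 9 and a pattern shared by all four patients. The simulated rates depend on assumed noise and shift sizes. The Bonferroni result covers one table only; nothing is claimed about the other two. The primary endpoint, safety, is unaffected, as are the efficacy values themselves. What changes is the inferential claim that may be attached to them.

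**What to change.** 1. Remove the three Friedman p values. Alternatively, label them post hoc, cite section 13.3, and state only that values differed between at least two visits.
2. Delete the sentence saying that the ANOVA results are consistent with the Friedman test.
3. Base the efficacy description on each patient's values: the time course for LSCD stage and opacification and the change from baseline for visual acuity, as section 13.2.4 plans. Add the preoperative-to-Week-52 change for all three outcomes; for stage and opacification this goes beyond 13.2.4 and should be marked as an addition.
4. If a preoperative-versus-Week-52 test is kept, use one contrast per outcome with the patient as the unit, label it post hoc, and state that an exact two-sided sign-flip p with four patients cannot fall below 0.125.

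These are text and table edits that need no new data. The price is the loss of three p values below 0.05, and an exact test in their place could not reach that level.

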### 15. Outcome evaluation

The safety of iCEPS transplantation was assessed by collecting all adverse events, including immunological rejection and tumour formation, during the 52-week follow-up period subsequent to transplantation (Table S8). An additional one-year monitoring period collected adverse events up to week 104 (Table S9). Secondary endpoints were as follows: 1) the LSCD stage, 2) corrected distance visual acuity using a decimal visual acuity chart and an ETDRS chart, 3) the degree of corneal opacification, 4) the severity of corneal epithelial defect, 5) the degree of corneal neovascularisation, 6) the degree of symblepharon, 7) subjective symptoms, and 8) QOL as evaluated by NEI VFQ-25. All were reported for the 52-week follow up, with some recorded at the 104-week endpoint of the additional monitoring period as described in the following figures and tables.

- 1) The LSCD stage: severity was determined by slit-lamp microscopy using the severity classification of LSCD (Figure S5 and S7, Table S10).
- 2) Corrected distance visual acuity: visual acuity was measured using the standard visual acuity table specified in JIS T 7309 (Landolt ring chart) converted to LogMAR (Table S11). Visual acuity was measured using the ETDRS visual acuity test chart (Tables S12 and S13).
- 3-1) The degree of corneal opacification: The cornea was divided radially into eight sections, and the degree of corneal opacification in each section was determined using slit-lamp microscopy (Table S14).
- Grade 0: The cornea is transparent, and the iris can be observed in detail.
- Grade 1: Details of the iris can be partially observed.
- Grade 2: The iris details cannot be clearly observed, and the rim of the pupil is scarcely observed.
- Grade 3: Neither the iris nor rim of the pupil are observed.
- 3-2) Corneal thickness: the cornea was radially divided into eight sections, and the corneal thickness in each section was measured using AS-OCT CASIA2 (Table S15).
- 3-3) Transparency of the corneal epithelium: a commercially available SS-OCT device (DRI OCT Triton, Topcon, Tokyo, Japan) was used to image the corneal area using 3 × 3 mm^2 volume scans. The average

OCT intensity was computed for the segmented epithelium layer within the eight selected distinct segments (Table S16).

3-4) Corneal epithelial thickness: the cornea was radially divided into eight sections, and the epithelial thickness was measured using RTvue-100 (Table S17).

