# 13.5 Procedures for Changing the Analysis Plan

If a change or addition to the analysis plan is made after the start of the research, the protocol will be revised. The circumstances that led to the change or addition to the analysis plan will be described in the clinical study report (CSR).

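### Supplementary Methods 18 reports significance tests on three of eight secondary endpoints although Protocol 13.3 rules such tests out, and the available text does not declare the departure, justify the choice of endpoints or adjust across them

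*Combined protocol and SAP*

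**What the plan says.** **Protocol.** Section 13.3 reads "No estimations or tests that would require setting of confidence coefficients or significance levels will be used in this research" and continues "Instead, descriptive methods will be used in analysis". Section 13.2.4 applies this to the secondary endpoints. For the graded outcomes, "A time course of severity will be shown in a table and line graph for the following items"; for corrected distance visual acuity (CDVA), "measured values and the magnitude of change from baseline over time will be shown in a table and line graph". QOL gets summary statistics. Section 13.5 adds: "If a change or addition to the analysis plan is made after the start of the research, the protocol will be revised". It also sends the explanation of any change to the clinical study report (CSR). The revision history runs to Ver. 2.2 and lists no change to section 13.

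**Supplementary Methods 18.** LSCD stage, CDVA and corneal opacification were compared before and after surgery "at each visit of four patients using the Friedman test and a repeated measures ANOVA". The Friedman test "demonstrated that there were significant differences in the LSCD stage, CDVA and corneal opacification values throughout the follow-up period", with p values of 0.001, 0.03 and 0.01 in that order. The repeated measures ANOVA compares the preoperative value with eight postoperative visits, using Bonferroni for multiple comparisons. Tables S32 to S34 give F on (1, 3) degrees of freedom with unadjusted P values, and asterisks mark significant visits. The section says the ANOVA data agree with the Friedman results.

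**Endpoints.** The synopsis and Protocol 9.2 list eight secondary endpoints. Supplementary Methods 15 describes one of them as "corrected distance visual acuity using a decimal visual acuity chart and an ETDRS chart".

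**The concern.** A plan that excludes significance tests and a methods section that reports them cannot both describe the analysis. Adding analyses is legitimate if it is declared. In the available text, Section 18 does not say that the tests were outside the plan. Its one use of the term post hoc refers to pairwise comparisons following the ANOVA. No reason is given for testing these three endpoints and not the other five, or for using the Landolt rather than the ETDRS acuity.

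At stake is what may be concluded on efficacy. Section 18 says that significant differences were demonstrated, in an uncontrolled study of four patients whose plan was descriptive. Whether p = 0.03 for CDVA supports that wording depends on which tests are counted together, and the available text does not settle this.

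**Working it through.** **Inputs.** Friedman p values from Supplementary Methods 18: LSCD stage 0.001, CDVA 0.03, opacification 0.01. The eight F(1, 3) and P values come from the last ANOVA table before the Supplementary References. By its position this is probably Table S34 (opacification), but its title is not in the available text. Alpha is assumed to be 0.05.

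**1. Reproduce the printed ANOVA row.** P is the upper tail of F(1, 3); the adjusted value is 8 × P for the eight visits.

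| F | P, recomputed | P, printed | 8 × P |
|---|---|---|---|
| 27.99 (three visits) | 0.0132 | 0.01 | 0.105 |
| 15.21 (one visit) | 0.0299 | 0.03 | 0.239 |
| 16.36 (three visits) | 0.0272 | 0.03 | 0.218 |
| 17.64 (one visit) | 0.0246 | 0.02 | 0.197 |

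All eight printed values reproduce. To reach 0.05 after Bonferroni over eight, P must be below 0.05/8 = 0.00625, so F must exceed 47.5. The largest F is 27.99, and no visit in this row qualifies.

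**2. Adjust the Friedman p values across endpoints.** They cannot be recomputed, because the patient-level tables are not in the available text, so they are taken as printed. Bonferroni multiplies each p by the family size m. Holm multiplies the smallest by m, the next by m − 1 and so on, and keeps the running maximum. For m = 7 or 8, Holm is worked with the untested p values taken as larger than 0.03.

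The family of eight is all listed secondary endpoints. The family of seven omits QOL, which Protocol 8.6 schedules only at screening, Day 0, and Week 52 or discontinuation.

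| Rule | LSCD stage | Opacification | CDVA |
|---|---|---|---|
| Holm, m = 3 | 0.003 | 2 × 0.01 = 0.02 | 0.03 |
| Bonferroni, m = 3 | 0.003 | 0.03 | 0.09 |
| Holm, m = 7 | 0.007 | 6 × 0.01 = 0.06 | 5 × 0.03 = 0.15 |
| Bonferroni, m = 7 | 0.007 | 0.07 | 0.21 |
| Holm, m = 8 | 0.008 | 7 × 0.01 = 0.07 | 6 × 0.03 = 0.18 |
| Bonferroni, m = 8 | 0.008 | 0.08 | 0.24 |

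**3. Allow for rounding.**
- Opacification, printed 0.01, lies between 0.005 and 0.015. Over seven or eight endpoints it runs from 6 × 0.005 = 0.03 to 8 × 0.015 = 0.12, on both sides of 0.05.
- CDVA, printed 0.03, lies between 0.025 and 0.035. Over seven or eight it is at least 5 × 0.025 = 0.125.
- LSCD stage, printed 0.001, lies between 0.0005 and 0.0015. It is at most 8 × 0.0015 = 0.012.

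**The case against.** **Efficacy was only exploratory.** Supplementary Methods 1 makes safety primary and efficacy a matter of exploring feasibility, and Section 18 concedes that normality is hard to show with four cases. A reader might infer that the authors claim confirmed efficacy. The documents do not say so, and only the verb demonstrated points that way. The objection limits the harm; it does not reconcile Section 18 with 13.3.

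**Alpha may be stated elsewhere.** Most of Tables S32 to S34 is not in the available text, and a key to the asterisk would normally sit there. It cannot be said that no alpha was set. Likewise the CSR, where 13.5 puts the explanation, is not available. This stands.

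**Bonferroni was used.** It was, across comparisons within the ANOVA, and the section deserves credit for that. It does not reach across endpoints.

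**No error inflation is shown beyond the tests run.** A reader might compute 1 − 0.95^8 = 0.337 as the chance of a false positive over eight independent tests. That presumes the three endpoints were picked after seeing results, or that other tests were run and left out. Nothing in the documents shows either.

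**The omnibus and visit results can differ.** A significant Friedman test does not require any single visit to pass Bonferroni, so the ANOVA row does not refute the Friedman result. The row as available carries no asterisk, so misflagged visits cannot be inferred. What stands is that the row gives the stated agreement no support at visit level after the section's own correction.

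**The acuity scale.** Section 18 names decimal acuity and the title of Table S33 names LogMAR. Friedman uses ranks, so this conversion does not change its result. The choice that needs a reason is Landolt or ETDRS.

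**Conclusion.** The point holds as an undeclared departure from Protocol 13.3 and 13.5, so far as the available text goes. Its size, at an assumed alpha of 0.05:
- LSCD stage survives every rule tried.
- CDVA survives only Holm over the three tests. It fails Bonferroni over three (0.09), and fails over seven or eight endpoints if the untested p values are larger.
- Opacification survives both rules over three. Over seven or eight it is undecided (0.03 to 0.12).

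A reader might go further and declare opacification non-significant. The printed p values do not support that: rounding straddles 0.05, and small p values among the untested endpoints would lower the Holm multiplier. The same caution applies to CDVA under Holm.

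The p values are also only roughly calibrated with four patients. Simulating the Friedman chi-square test with four patients and nine time points (an assumed layout of baseline plus eight visits) gave a true size at nominal 0.05 of about 0.03 under independence. With visit-to-visit correlation of 0.5 it was 0.045, and with 0.9 about 0.08. The error can go either way, which is a further reason not to rest a claim on these values.

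**What to change.** **Preferred: follow 13.3.** In Section 18 and Tables S32 to S34, replace the significance wording and asterisks with individual and median changes from the Day 0 baseline.

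**If the tests are kept:**
- state that they were not in the protocol and are exploratory, and describe the departure in the CSR under 13.5;
- state the alpha, why these three endpoints were chosen, and why Landolt rather than ETDRS acuity;
- show the Bonferroni-adjusted P value for each visit beside the unadjusted one;
- define the family of endpoints, saying how QOL, the six symptom items and the eight corneal sections are counted, and report p values adjusted across it.

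Either way, do not describe efficacy on any endpoint as statistically demonstrated.

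**Cost.** Wording changes in one section and three tables, a paragraph in the CSR and, if the tests stay, a few extra runs on data already collected. The efficacy statement becomes less favourable. The primary safety endpoint is unaffected.
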